Official Title of the Study:

A Prospective Randomized Clinical Trial to Evaluate the Impact of Intraoperative Ventilation with High Oxygen Content on the Extent of Postoperative Pneumocephalus in Patients Undergoing Craniotomies

NCT number: NCT02722928

Last approved continuing review on: 08MAR2018

IRB protocol number: 2015H0032

- Initial submission approved on: 27JAN2015
- IRB confirmed closure date: 26DEC2018

Objectives*Primary Objective*

We compared the rate of occurrence and volume of postoperative pneumocephalus in patients undergoing craniotomies (hemispheric or posterior cranial fossa tumors and microvascular decompression) and receiving intraoperative ventilation with pure oxygen versus a conventional air/oxygen 1:1 mixture during the last stage of surgery (hemostasis and wound closure)

Secondary Objectives

We compared the incidence and volume of postoperative pneumocephalus in patients undergoing surgery in sitting and supine positions. Furthermore, we compared postoperative neurological outcomes and intensive care unit length of stay among neurosurgical patients (posterior cranial fossa tumors, supratentorial tumors, and transsphenoidal /endoscopic procedures)

Study Design

We conducted a prospective randomized single-blinded study at The Ohio State University Wexner Medical Center enrolling patients (≥ 18 years) with an American Society of Anesthesiologists (ASA) physical status of II–IV undergoing neurosurgeries (supra- and infratentorial tumors such as astrocytomas and glioblastoma multiforme, and microvascular decompression) in sitting, prone, lateral, park bench, and other positions.

Sample Size and Statistical Analysis

We estimated that a sample size of 80 patients per group would confer a greater than 80% power to detect a 20% decrease in volume in the intervention group with an alpha of 0.05 considering a mean pneumocephalus volume of 87 ml in the control group (standard deviation of 40). The sample size was estimated based on published data. Our proposed intervention is considered harmless, being applied routinely in perioperative settings. No intervention-related adverse events were expected during the study.

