Categorical variables were reported as frequencies and percentages and compared between randomization groups using Chi-square tests or Fisher's exact tests where relevant. Continuous variables were reported as means and standard deviations or medians and interquartile ranges and compared between randomization groups using Student's t-tests or Wilcoxon rank sum tests where relevant. Hypothesis testing was conducted at a 5% type 1 error rate ($\alpha=0.05$). All statistical analyses were performed using SAS version 9.4 (SAS Institute, Cary, NC).

Randomization

The study was planned and conducted according to all the required institutional and state regulations related to clinical research. Patients were randomly distributed (random table) into two groups:

- Control Group (A): received controlled ventilation throughout the surgery with a conventional air/oxygen 1:1 gas mixture (FiO_2 60%)
- Interventional Group (B): received controlled ventilation with a conventional air/oxygen 1:1 gas mixture from the beginning of the surgery and during the tumor removal phase. However, patients in group B were switched to controlled ventilation with

100% O₂ once the tumor resection was completed and hemostasis started until extubation

Study Procedures

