Both groups received supplemental oxygen via nasal cannula as a standard of care during the early postoperative period. A standard CT scan was performed within 6 hours post-surgery for both groups. CT scans were assessed and interpreted by a blinded radiologist in order to diagnose the frequency and the extent of postoperative pneumocephalus (quantification). TeraRecon Intuition software version 4.4.11.265.8092 was used, retrieving the CT scan data from the system and loading it into the software program. All CT data maintained a 1 mm slice increment. The air in the skull was identified and circled using a region of interest (ROI) tool. The area defined for measurements applied in this study was within the skull in any space occupied by brain. This excluded any air trapped between the bone from graft placement or between the skin and the skull. Once all the visually identified areas of “air” were circled and then selected within the skull, a Hounsfield unit (HU) threshold tool was used to remove any excluded tissue. The setting of -150 HU or less was applied, and the selected areas were presented in 2D and 3D. Only the areas identified within the ROI accounted for the 3D image. The volume was calculated in cm³ using the software presented by clicking the “volume” measurement tool. Considering similarity of the groups and randomization, it was expected that the duration of the last part of surgery and the lapsing time from the end of surgery to postoperative CT acquisition to be the same for the control and treatment groups. The following data was considered for intergroup analysis and selection bias exclusion: demographics (age, gender, weight, and body mass index), oxygen inhalation time, the period of time elapsed from the end of surgery to CT scan completion. The occurrence of adverse events and neurological status were assessed before the CT scan and compared with the baseline evaluation. Stage 1 was defined as the interval of time (minutes) measured from skin incision to the onset of hemostasis (i.e. after tumor removal). Stage 2 was defined as the interval of time (minutes) measured from the onset of hemostasis to incision closure. We conducted study intervention (for group B) during stage 2.

DISCUSSION

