Our prospective randomized study is the first to examine the prophylactic effect of normobaric hyperoxygenation on limiting the extension of postoperative pneumocephalus volume in patients undergoing elective neurosurgery. A total of 70 patients were included into our final analysis. The study showed no pneumocephalus volume reduction when higher oxygen concentration (FiO₂ 100% vs 60%) was used prophylactically during the last stage of surgery in patients undergoing craniotomy (p= 0.47). We estimated that our intervention would produce a 20% decrease in pneumocephalus volume for the interventional group. However, after enrolling 105 (N=105) patients, an unanticipated blinded analysis showed that the variability relative to the pneumocephalus volume mean was much higher than initially assumed based on published data. Therefore, we determined that our study was underpowered and an unfeasible number of patients would have been required (N>400 patients/group) to be enrolled in order to detect the expected difference between groups.

Figure 1. CONSORT Flow Diagram

[figure not shown]

Table 1. Demographic and Clinical Variables

| Variable | Control n= 39 | Intervention n= 31 | p value |
|-------------------------------------|--------------------------|-------------------------------|----------------|
| Age (mean ± SD) | 46.69 (14.21) | 50.81 (13.28) | 0.2198 |
| Gender n (%) | | | |
| • Female | 23 (58.97) | 14 (45.16) | 0.2501 |
| • Male | 16 (41.03) | 17 (54.84) | |
| Race n (%) | | | |
| • White | 36 (92.31) | 27 (87.10) | 0.6916 |
| • African-American | 3 (7.69) | 4 (12.90) | |
| Biometrics mean ± SD | | | |
| • Weight (Kg ± SD) | 89.00 (21.69) | 94.00 (17.67) | 0.3034 |
| • Height (cm ± SD) | 168.31 (10.29) | 172.30 (10.90) | 0.1208 |
| • BMI (Kg/m ² ± SD) | 31.35 (7.42) | 31.94 (6.64) | 0.7301 |
| ASA n (%) | | | |
| • I | 0 (0.00) | 1 (3.23) | 0.8874 |
| • II | 12 (30.77) | 9 (29.03) | |
| • III | 26 (66.67) | 20 (64.52) | |
| • IV | 1 (2.56) | 1 (3.23) | |
| Preoperative Diagnosis n (%) | | | |
| • Supratentorial lesion | 25 (64.10) | 21 (67.74) | 0.7500 |
| • Infratentorial lesion | 14 (35.90) | 10 (32.26) | |

n = number of patients; ASA = American Society of Anesthesiologists

Table 2. Perioperative Variables

| Variable | Control n= 39 | Intervention n= 31 | p value |
|---|-----------------------------|-------------------------------|--------------------|
| Surgical Positioning n (%) | | | |
| Sitting | 1 (2.56) | 0 (0.00) | 0.1233 |

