| Semi-sitting | 0 (0.00) | 0 (0.00) | |
| Prone | 10 (25.64) | 3 (9.68) | |
| Lateral | 7 (17.95) | 11 (35.48) | |
| Park bench | 0 (0.00) | 0 (0.00) | |
| Supine | 21 (53.85) | 17 (54.84) | |
| Procedure Performed n (%) | | | |
| Conventional Anterior Fossa | 23 (58.97) | 16 (51.61) | 0.1535 |
| Conventional Posterior Fossa | 15 (38.46) | 11 (35.48) | |
| Conventional Middle Fossa | 0 (0.00) | 3 (9.68) | |
| Minimally Invasive Anterior Fossa | 0 (0.00) | 1 (3.23) | |
| Minimally Invasive Middle | 1 (2.56) | 0 (0.00) | |
| Ventilatory parameters | | | |
| beginning of stage 2 [median and IQR] | | | |
| Ppeak (cm H ₂ O) | 21.0 [19.0 – 25.0] | 22.0 [20.0 – 25.0] | 0.3734 |
| PEEP (cm H ₂ O) | 4.9 [4.0 – 5.0] | 5.1 [4.4 – 7.0] | 0.0215 |
| EtCO ₂ (mm Hg) | 29.0 [28.0 – 32.0] | 30.00 [28.0 – 32.0] | 0.8726 |
| Length of stage 1 [median and IQR] | 177.0 [140.0 – 223.0] | 256.0 [145.0 – 344.0] | 0.0596 |
| Length of stage 2 [median and IQR] | 49.0 [34.00 – 63.0] | 55.0 [39.0 – 68.0] | 0.3688 |
| Postoperative Recovery Location | | | |
| PACU | 6 (15.38) | 3 (9.68) | 0.7214 |
| SICU | 33 (84.62) | 28 (90.32) | |
| Length of PACU stay (min ± SD) | 344.67 (455.51) | 178.33 (147.60) | 0.5683 |
| Length of SICU stay (min ± SD) | 1,380.0 [1,112.0 – 2,096.0] | 1,524.5 [1,312.0 – 2,814.5] | 0.1880 |
| End of Surgery - CT scan interval time in minutes [median and IQR] | 89.0 [61.0 – 125.0] | 80.0 [62.0 – 127.0] | 0.8229 |
| Postoperative pneumocephalus in cm³ [median and IQR] | 9.65 [3.61 – 23.20] | 7.06 [2.70 – 20.1] | 0.4768 |

n= number of patients; *Ppeak*= peak inspiratory pressure; *PEEP*= positive end-expiratory pressure; *EtCO₂*= end-tidal CO₂; *PACU*= post-anesthesia care unit; *SICU*= surgical intensive care unit; *CT*= computed tomography

Table 3. *Postoperative Pneumocephalus Volume in cm³ [median and IQR] according to Procedure Performed*

| Conventional Anterior Fossa | Control n= 23 | Intervention n= 16 | p value |
|-------------------------------------|-------------------------|------------------------------|----------------|
| | 17.40 [6.89 – 24.40] | 13.95 [4.82 – 22.15] | 0.4797 |
| Conventional Posterior Fossa | Control n= 15 | Intervention n= 11 | p value |
| | 4.38 [0.81 – 10.50] | 4.00 [0.60 – 13.00] | 0.8775 |

Table 4. *SICU LOS according to Procedure Performed (median min [IQR]).*

| Conventional Anterior Fossa | Control n= 23 | Intervention n= 16 | p value |

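### The volume comparison ignores lesion location, a recorded preoperative factor whose proxy is strongly prognostic; using it is a free but modest gain in precision that leaves the result null.

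*Combined protocol and SAP*

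**What the plan says.** Sample Size and Statistical Analysis gives one rule for every continuous variable: compare the arms by Student's "t-tests or Wilcoxon rank sum tests where relevant". No covariate, stratum or model is named anywhere. Study Procedures lists the variables "considered for intergroup analysis and selection bias exclusion: demographics (age, gender, weight, and body mass index), oxygen inhalation time", together with the time from end of surgery to CT; lesion location is not among them.

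Location does appear elsewhere:

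- The Primary Objective describes the population as "hemispheric or posterior cranial fossa tumors and microvascular decompression".
- The Secondary Objectives name "posterior cranial fossa tumors, supratentorial tumors, and transsphenoidal /endoscopic procedures" for neurological outcome and intensive care stay.
- Table 1 gives the preoperative diagnosis by arm: "Supratentorial lesion | 25 (64.10) | 21 (67.74) | 0.7500", with 14 and 10 infratentorial lesions making up the rest of the 39 and 31 patients. It is used only for a balance test.

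The overall volume row in Table 2 is unadjusted: "9.65 [3.61 – 23.20] | 7.06 [2.70 – 20.1] | 0.4768". Table 3 splits volume by procedure performed and tests anterior and posterior fossa separately. It gives no combined result. The Discussion attributes the lack of power to variability well above what was assumed, and puts the requirement above 400 per group.

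**The concern.** When a factor known before surgery explains a good part of the spread in the outcome, a test that ignores it leaves that spread in the error term. This trial ended because of excess variability, so an available source of explained variability is worth using. At stake is the precision of the primary comparison. Randomisation protects validity, and the arms were balanced on location (p = 0.7500), so bias is not in question.

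**Working it through.** **The plan's own figure.** A 20% decrease from 87 ml is 17.4 ml. With SD 40 and 80 per group, 17.4 / (40 × √(2/80)) = 2.751, and Φ(2.751 − 1.960) = 78.6% two-sided (86.6% one-sided). The stated figure of more than 80% is close, but is met literally only one-sided. At 80% power, 400 per group for a 20% difference implies a coefficient of variation of about 1.01, against 40/87 = 0.46 as planned.

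**Strength of location (Table 3, procedure site).** Anterior/posterior median ratios:

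- control: 17.40/4.38 = 3.97
- intervention: 13.95/4.00 = 3.49

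Share of log-volume variance explained = p(1−p) × ln(ratio)² / SD², where p is the posterior share and SD = ln(Q3/Q1)/1.349 from the Table 2 overall quartiles:

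- control: (15/38)(23/38) × ln(3.97)² = 0.455; SD = ln(23.20/3.61)/1.349 = 1.379; 0.455/1.379² = 0.239
- intervention: (11/27)(16/27) × ln(3.49)² = 0.377; SD = ln(20.1/2.70)/1.349 = 1.488; 0.377/1.488² = 0.170

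Using the within-site quartiles of Table 3 instead gives 0.189 and 0.116.

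**Combined result from Table 3.** This treats both as two-sided Wilcoxon p-values in the same direction, as the medians are.

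- z = 0.707 (p = 0.4797) and 0.154 (p = 0.8775)
- weights mn/(N+1): 23×16/40 = 9.20 and 15×11/27 = 6.11
- z = (√9.20 × 0.707 + √6.11 × 0.154) / √(9.20 + 6.11) = 0.645, p = 0.52

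This covers 23+16+15+11 = 65 of 70 patients. Other approximations from the same quartiles give p between 0.43 and 0.66.

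**Power by simulation.** There were 20 scenarios: Table 3 quartiles of the control or intervention arm; five tail shapes (lognormal, exponential, or piecewise with assumed maxima of 60/40, 100/80 or 200/150 cm³ for anterior/posterior); and a posterior share of 24/70 or 40%. The tails are assumptions, since the documents give only quartiles. As a check, the control piecewise and exponential scenarios give pooled quartiles of 3.5, 10.6 and 21.2-24.0, against 3.61, 9.65 and 23.20 in Table 2.

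| Setting | Plain Wilcoxon | Stratified Wilcoxon |
|---|---|---|
| 80 per arm, 20% reduction in both sites | 13.7-25.8% | 16.4-33.3% (higher in 20 of 20) |
| 39/31, same effect | 8.5-13.0% | 9.4-15.9% |
| 80 per arm, effect only anterior | 9.0-16.6% | 10.9-21.7% |
| 80 per arm, effect only posterior | 5.2-6.8% | 5.5-6.6% |
| Patients per arm for 80% power | 365-859 | 270-674 |

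Scenario by scenario, the stratified test needs 15-38% fewer patients. Its type I error was 4.6-5.4%.

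**Diagnosis versus procedure.** Infratentorial diagnoses number 14 and 10; posterior fossa procedures 15 and 11. The net difference of 2 in 70 is only a lower bound on disagreement. If the two disagree in 10% of patients, the requirement is 302-729 per arm (saving 9-27%); if in 20%, 331-786 (saving 5-17%).

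**Mean comparison.** Adjusting a comparison of means for location saves 0.1-16.5%, and almost nothing when the tails are long. The raw t-test beat the stratified Wilcoxon in 9 of 20 scenarios, with short tails, and lost with long ones. No ranking between the two is claimed.

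**The case against.** An unadjusted two-arm comparison is a legitimate choice in a randomised trial, and nothing here is biased. At the analysed size the gain is a few points of power at most, and no conclusion changes. The figure above 400 per group comes from a calculation on means, where adjustment may bring almost nothing. The factor to be used, preoperative diagnosis, has no volume data in the documents; all the evidence concerns procedure site and comes from the trial's own results. The objectives name location for the population and for other outcomes, whereas for volume they name position. Table 3 already lets a reader see the site effect.

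Most of this stands, and it limits the size of the point. The 15-38% saving belongs to the rank test only, and it does not carry over to the figure above 400. The proxy and the effect pattern are real uncertainties: if only posterior cases benefit, there is no gain.

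Three parts do not remove the point. Medians and IQRs in Tables 2 and 3 suggest that a rank test was the working analysis, and there the stratified version was the stronger in every scenario with a common effect. Position offers no substitute as the objectives frame it, since Table 2 has one sitting patient; and if the site contrast partly reflects position, site still predicts volume. Finally, two separate small tests in 65 patients are not a combined estimate in 70.

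**Conclusion.** The point holds, at modest size. The plan leaves out a recorded pre-treatment factor whose close proxy explains roughly 12-24% of the variance in log volume. For a rank test with a common 20% reduction, stratifying adds 2.5-7.5 points of power at 80 per arm and about 0-3 points at 39/31. The smallest stratified requirement, 270 per arm, is still 3.4 times the planned 80, so the trial would not have been rescued. The result stays null, at about p = 0.52.

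These figures rest on assumed tails, on a similar proportional effect in both locations, and on diagnosis agreeing well with procedure site. This is an improvement the plan should make, not an error that invalidates the analysis. Confidence in the size is medium.

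**What to change.** - Replace the plain Wilcoxon test for volume with a Wilcoxon test stratified by preoperative diagnosis, supratentorial versus infratentorial (van Elteren). Diagnosis is preferable to procedure performed because it is fixed before surgery and covers all 70 patients.
- Report a location-stratified Hodges-Lehmann difference in cm³ with a 95% confidence interval.
- If a comparison of means is chosen instead, adjust it for location.
- Tabulate volume by diagnosis and arm, so that the strength of the stratum can be seen, and present Table 3 as descriptive.

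The cost is a sentence in the analysis plan and one stratified procedure call in SAS; the interval may need a short program that inverts the same test. No new patients, scans or data are needed. For the completed trial the analysis must be labelled post hoc and shown beside the reported p = 0.4768.

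### The Discussion reads a non-significant p-value in an underpowered trial as showing no volume reduction, with no estimate or confidence interval for the difference

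*Combined protocol and SAP*

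**What the plan says.** - **Discussion, the conclusion.** "The study showed no pneumocephalus volume reduction when higher oxygen concentration" was applied in the last stage of surgery, with p = 0.47 in parentheses as the only support.
- **Discussion, the analysis set.** "A total of 70 patients were included into our final analysis". The tables split these into 39 control and 31 intervention patients.
- **Discussion, the caveat.** After 105 patients had been enrolled, a blinded look found that "the variability relative to the pneumocephalus volume mean was much higher than initially assumed based on published data". The paragraph ends: "we determined that our study was underpowered and an unfeasible number of patients would have been required", put at more than 400 per group.
- **Sample Size and Statistical Analysis, the target.** With 80 per group and an assumed SD of 40, power was put above 80%. The effect sought is worded as follows: "detect a 20% decrease in volume in the intervention group with an alpha of 0.05 considering a mean pneumocephalus volume of 87 ml".
- **Table 2, postoperative pneumocephalus in cm³, median [IQR], control then intervention, then p-value.** "9.65 [3.61 – 23.20] | 7.06 [2.70 – 20.1] | 0.4768".
- **Sample Size and Statistical Analysis, the method.** "Continuous variables were reported as means and standard deviations or medians and interquartile ranges and compared between randomization groups" by t-test or Wilcoxon rank sum test. No effect estimate or interval is planned, and none is reported in any table.

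**The concern.** A non-significant test does not show that an effect is absent. It shows that the data are compatible with no effect, and whether they are also compatible with a worthwhile effect depends on the width of the interval. The document gives no interval, so the reader cannot tell which effects the trial rules out.

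The sentence also sits awkwardly with the trial's own figures. The intervention median is 27% lower than control, which is numerically beyond the 20% target. That is not evidence of benefit, but *no reduction* is neither a description of the data nor an inference they support.

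This is the result statement for the volume part of the primary objective. Anyone who takes that sentence alone would count the trial as negative for the effect it was designed to detect.

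**Working it through.** **Inputs.** From Table 2: medians and quartiles 9.65 [3.61, 23.20] (n = 39) and 7.06 [2.70, 20.1] (n = 31), p = 0.4768. From the sample-size section: mean 87 ml, SD 40, 20% decrease, alpha 0.05, 80 per group. From the Discussion: more than 400 per group. The test is assumed two-sided, since sidedness is not stated.

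**1. The plan's own power figure.** Difference = 0.20 × 87 = 17.4 ml. SE = 40 × √(2/80) = 6.325. Power = Φ(17.4/6.325 − 1.96) = Φ(0.79) = 78.6%. This is close to the stated figure, though slightly under 80% (a one-sided test gives 86.6%). The planning inputs are therefore understood correctly.

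**2. Observed contrast.** Ratio of medians = 7.06/9.65 = 0.732, log = −0.3125. Difference = −2.59 cm³.

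**3. Spread.** The quartiles are right-skewed on the raw scale: control lies 6.04 below and 13.55 above the median, intervention 4.36 below and 13.04 above. The log scale is therefore used, with log SD = ln(Q3/Q1)/1.349:
- control: ln(23.20/3.61)/1.349 = 1.379
- intervention: ln(20.1/2.70)/1.349 = 1.488

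**4. Approximate 95% limits for the ratio,** exp(−0.3125 ± 1.96 × SE):

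| Basis | SE (log) | Limits | Implied p |
|---|---|---|---|
| Geometric means: √(1.379²/39 + 1.488²/31) | 0.347 | 0.37 to 1.44 | 0.37 |
| Medians: 0.347 × √(π/2) | 0.4345 | 0.31 to 1.71 | 0.47 |
| From p = 0.4768: z = 0.711, SE = 0.3125/0.711 | 0.439 | 0.31 to 1.73 | 0.4768 (by construction) |

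All three include 1.00 and 0.80. They share the same centre and a log-scale model, so they are variants of one approximation and not independent confirmations. The third treats the reported p-value as a z-test of the log ratio; the document does not name the test used.

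**5. Power at 39 and 31 for a true 20% reduction** (noncentral t):

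| Variability assumed | Power | Chance of missing it |
|---|---|---|
| Observed log SD 1.379 to 1.488, effect ln(0.8) | 10% to 9% | about 90% |
| CV implied by 400 per group at 80% power: 0.2 × √(400/2)/(1.96 + 0.84) = 1.01 | 13% | 87% |
| Planning SD of 40, difference 17.4 ml | 43% | 57% |

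Simulated Wilcoxon tests on log-normal data give 10.0% and 9.2% for the first row, so the choice of test does not matter here.

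**6. Sample size on the observed log spread.** 80% power for a ratio of 0.80 needs about 600 (SD 1.379) to 700 (SD 1.488) per group. This does not conflict with the document's figure of more than 400, but that figure is open-ended, so the agreement is weak support.

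**The case against.** The strongest reply is that the paragraph already handles the point. Three sentences after the definite statement, it says the study was underpowered and that more than 400 per group would be needed to detect the expected difference. Table 2 prints both medians, both IQRs and the exact p-value, so nothing is concealed. On this view what remains is one over-strong sentence in a closed study, and the fault is one of reporting.

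The mitigation is real. But the caveat explains why recruitment could not reach the required size; it does not say that the result is inconclusive or that a 20% reduction remains possible. An acknowledged lack of power makes a definite negative harder to defend.

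The technical objections also have substance:
- **Log-normality is only partly supported.** Pooled quartiles are roughly symmetric on the log scale (log distances below/above the median 0.98/0.88 in control, 0.96/1.05 in intervention). Within the procedures in Table 3 they are left-skewed: anterior fossa 0.93/0.34 and 1.06/0.46, posterior fossa 1.69/0.87 and 1.90/1.18.
- **Zero volumes are possible,** because occurrence is itself part of the primary objective.
- **The power level behind the figure of more than 400 is not given.** If it was 90%, the implied CV is 0.87 and power at 39 and 31 is about 16%.
- **A confidence interval on 70 patients reflects sampling error only,** although 105 were enrolled.

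These points weaken the second decimal of the limits. They do not change the finding that the limits span both 0.80 and 1.00, or that power was low.

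**Conclusion.** The concern holds. The statement that there was no volume reduction goes beyond what p = 0.4768 with 39 and 31 patients can support. The observed ratio is 0.73, with rough limits of about 0.3–0.4 to 1.4–1.7, and a true 20% reduction would have been missed about nine times in ten on the observed or implied variability. Even at the planning SD it would have been missed more often than not. The trial is therefore neither negative nor positive for its 20% target.

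The limits assume log-normal volumes with no zeros, SDs taken from published quartiles and a two-sided 5% test; patient-level data are not given. The conclusion on wording does not depend on that model, because the document's own requirement of more than 400 per group, set against 39 and 31 analysed, leads to the same place. Because the authors disclose the low power, this is something that should be fixed and not a fatal fault.

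**What to change.** Replace the sentence with: *No statistically significant difference in pneumocephalus volume was detected (p = 0.48); the study was underpowered and the result is inconclusive with respect to the targeted 20% reduction.* The value 0.4768 rounds to 0.48, whereas the text prints 0.47.

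Add an estimate of the difference with a 95% confidence interval from the patient data, labelled post hoc: a Hodges–Lehmann shift, or a ratio of geometric means if there are no zero volumes. Check the word *inconclusive* against that interval before finalising. Judge the interval against 20% of the observed control level and not against the planning difference, since 17.4 ml exceeds the whole observed control median of 9.65 cm³. Note beside it that the interval describes sampling error in the 70 analysed patients only.

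The cost is one sentence and one additional SAS estimate from data already held. The conclusion becomes less definite, and the estimate must carry the post hoc label because the study is closed and the results are known.
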